7.2 Number of Patients and Sites

Approximately 150 patients are planned to be randomized at approximately 15 study centers.

7.3 Method of Treatment Assignment and Blinding

Patients will be randomized in a 1:1:1 ratio to 1 mg AZ-010, 3 mg AZ-010, or matching Staccato Placebo (Staccato device without drug coating). Randomization will be stratified by duration of the patient's typical CVS episode into one of the following two categories:

- 1. Typical episode of CVS lasts 24 hrs or less from the first vomiting/retching event;
- 2. Typical episode of CVS lasts greater than 24 hrs from the first vomiting/retching event.

The randomization schedule will be generated prior to study start. All study patients, Investigators, and site study staff will be blinded to study medication assignment. Devices and packaging of AZ-010 and placebo be identical in appearance.

7.4 Rationale for Study Design, Doses, and Primary Endpoint

Double-blind, randomized, placebo-controlled studies are considered optimal for obtaining unbiased estimates of the efficacy and safety of investigational products. There have been no double-blind, randomized, placebo-controlled studies assessing the acute treatment of CVS in adults prior to this trial.

CVS is generally described as consisting of four phases. The *hyperemesis phase* usually starts from the early hours of the morning to noon, and is characterized by intense persistent nausea and repeated vomiting. The vomiting frequency can be up to eight times every hour (Fleisher et al, 2005). This can last for 1–7 days. Antiemetic agents have been reported to be a key component of support care for acute abortive treatment during the prodromal and emetic phases of CVS in adults (Abell et al, 2008). Abortive IV antiemetic agents such as the 5-HT₃ antagonists ondansetron at high doses and granisetron were reported for supportive treatment of acute vomiting episodes in CVS patients (Li and Misiewicz et al, 2003; Yang, 2010; Venkatasubramani, 2007).

Granisetron is a highly selective and potent 5-HT₃ receptor antagonist widely used for over twenty years as an effective antiemetic treatment (Blower, 2003). Because of its demonstrated effectiveness as an antiemetic treatment, granisetron was selected as the drug for development using the *Staccato* technology. One of the potential advantages of *Staccato* Granisetron (AZ-010) is rapid IV-like pharmacokinetics. In Phase 1 clinical trials with Staccato granisetron, mean peak plasma levels were achieved within minutes following inhalation. Because of this property, *Staccato* Granisetron offers flexibility compared to the IV route of administration since the patient can take the medication at home and achieve rapid drug exposure in a non-invasive way. In addition, as an abortive therapy, *Staccato* Granisetron offers an advantage to oral treatments that may be difficult to administer to an individual with uncontrolled vomiting.

IV administered granisetron at doses of 1 and 3 mg have been shown to be effective in treating nausea and vomiting. For example, a randomized, double-blind dose-ranging study for IV granisetron in the prevention of PONV found that a single dose of 1 mg or 3 mg resulted in a significant reduction in the numbers of patients experiencing postoperative nausea or vomiting during postoperative periods of 0–6 h and 0–24 h (78% and 77% of patients, respectively) (Wilson et al, 1996). Granisetron was well tolerated and the optimum dose was 1 mg. Consensus guidelines for the prevention of PONV in adults recommend treatment with 0.35–3 mg IV granisetron or 4 mg IV ondansetron at the end of surgery (Gan et al, 2014).

The selection of the 1 mg and 3 doses of AZ-010 for this study is supported by a Phase 1 study (AMDC 010-101) demonstrating the equivalence of PK exposure between 1 mg AZ-010 and 1 mg IV granisetron. In this crossover study conducted in healthy volunteers, mean peak and total granisetron exposure (C_{max} and AUC) were similar for both routes of administration with both treatments yielding peak exposure within 2 minutes. The half-life was the same with the IV and Staccato treatments at 10 hr. Consequently, given the importance of the 1 and 3 mg IV doses for granisetron in treating nausea and vomiting noted above and the PK equivalence of IV and *Staccato* granisetron, doses of 1 mg and 3 mg AZ-010 were selected for this study.

CVS is characterized by intense vomiting. The primary endpoint for this study is aimed at capturing the number of times the patient has vomited or retched (which will be considered the same as vomiting in the enumeration of events) in the time period specified post dosing. This endpoint is the most direct assessment of the primary symptom and will be recorded by the patient in the ePD.

7.5 Schedule of Events

The schedule of events is provided in Table 1.

Table 1:Schedule of Events

	Screening	ScreeningRandomization1Home Treatment Period2 (Up to 12 Weeks Post Randomization))	·
Event	Visit 1 (Up to Day -14)	Visit 2 (Day 1)	Schedule of Assessments for each Dosing Day (Up to 5 days)						
			Pre-0	0	2 h post dose	6 h post dose	12 h post dose	24 h	Visit 3
Informed consent	Х								
Eligibility assessment	Х	Х							
Demographics	Х								
Medical history	Х	Х							
Urine Drug and alcohol breath screen	Х								
Complete Physical Examination	Х	X ³							
Brief Physical Exam ⁴		Х							Х
Height	Х								
Weight	Х	Х							Х
Pregnancy test ⁵	Х								Х
Clinical laboratory testing ⁶	Х								Х
Serology (HIV, HBV, HCV)	Х								
COVID -19 test	Х	Х							
12-lead electrocardiogram	Х	X ⁷							Х
Vital signs	Х	Х							Х
Device Training		Х							
ePD Instructions		Х							
Randomization and assign Patient Kit		Х							
Study Medication Administration ⁸		Х		Х					
Patient activates ePD and study clock				Х					
Patient records number of discrete vomiting/retching events (ePD)				X	X				
VAS Assessments (ePD) ⁹					Х	Х	Х	Х	
RINVR Assessment (ePD)						Х	Х	Х	
Intensity of Attack Scale (ePD)					Х	Х	Х	Х	

	Screening	Randomization ¹	Home Treatment Period ² (Up to 12 Weeks Post Randomization)						Follow-Up /Termination
Event	Visit 1	Visit 2	Schedule of Assessments for each Dosing Day (Up to 5 days)						
	(Up to Day -14)		Pre-0	0	2 h post dose	6 h post dose	12 h post dose	24 h post dose	Visit 3
Prior Episode Questionnaire ePD								X	
24 Hour Vomiting and Retching Questionnaire				X-				X	
Reconciliation of Patient Kit									Х
Adverse events		Х		Х-				X	Х
Rescue Med or HCP Visit				Х-				Х	
Concomitant medications	Х	Х	X					X	Х

HBV = hepatitis B virus; HCV = hepatitis C virus

¹ Randomization/Day 1 may occur any time after eligibility has been confirmed at Screening. The Home Treatment Period cannot begin until the triplicate ECG and adverse event assessments are evaluated from Visit 2.

² Patients will be asked to enter responses into the ePD daily during the Home Treatment Period to ensure the device is charged and working.

³ Conducted upon return to clinic and prior to pre-test Study Medication administration only

⁴ Brief Physical exam will be symptom directed prior to patient discharge from the clinic

⁵ Serum pregnancy test only for females of childbearing potential

⁶ Includes hematology, serum chemistry, and urinalysis performed by the central lab.

⁷ ECG in triplicate at pre-dose and 2, 30, 60, 90, and 120 min post dosing with Study Medication

⁸ Study medication should be administered as closely as possible to start of vomiting; once per day up to 5 consecutive daily doses can be administered as long as the patient is still experiencing the same CVS episode

⁹ Includes separate scales for abdominal pain, nausea, and anxiety/panic

7.6 **Procedures for Protocol**

The following sections provide details regarding the procedures to be performed at each study visit. All of the following assessments should be made according to the Schedule of Events (Table 1).

7.6.1 Visit 1: Screening Visit

Patients will report to the clinical site for a screening examination between Day -14 and Day -1 and the patient and clinical staff will follow all appropriate COVID-19 safety procedures.

Prior to performing any study-related activities or evaluations, the patient must be thoroughly informed about all aspects of the study and sign the Informed Consent Form (ICF). Patients will sign the study-specific consent form prior to any screening procedure. A signed copy of the ICF should be provided to each consenting patient and with the original to be retained in the patient's study records.

For all study procedures, see the Schedule of Events (Table 1). The following information and procedures will be performed and documented as part of the Screening assessment:

- COVID-19 testing.
- Assessment of eligibility according to inclusion/exclusion criteria.
- Demographics, including sex, ethnic origin, date of birth.
- Medical history (with emphasis on history of CVS noted above) including query for baseline signs/symptoms.
- Review of prior and ongoing concomitant medications (taken in previous 30 days).
- Complete physical examination plus height and weight.
- Vital signs measured with the subject in a seated position (for at least 2 minutes prior), including blood pressure, pulse rate, respiration rate, pulse oximetry, and temperature.
- Standard 12-lead ECG.
- Blood samples for routine clinical labs (clinical chemistry, hematology).
- Blood samples for serology (HIV, and hepatitis B and C evaluations).
- Urine samples for urinalysis and drugs of abuse screen.
- Alcohol breath test.
- Serum pregnancy test (females of childbearing potential only).

Compliance with inclusion criteria (listed in Section 8.1) and exclusion criteria (listed in Section 8.2) will be verified against information collected and documented in the case report form (eCRF).

Once all inclusion criteria are met, exclusion criteria ruled out, and laboratory measurements obtained and reviewed, consenting patients are eligible for randomization into the study.

7.6.2 Visit 2: Randomization and Pre-test Study Medication Administration

On arrival at the clinical site, all patients will follow the appropriate COVID-19 procedures and undergo the following assessments, which will be documented:

- COVID-19 testing.
- Confirmation of eligibility according to inclusion/exclusion criteria.
- Update of medical history including query for any pre-treatment adverse events.
- Concomitant medication use since the Screening visit.
- Physical examination plus weight.
- Vital signs measured with the subject in a seated position (for at least 2 minutes prior), including blood pressure, pulse rate, respiration rate, pulse oximetry, and temperature.
- Randomization and assignment of Patient Kit.
- *Staccato* device training.
- ePD instructions and training.

Upon determination of continued eligibility from above, the patient will undergo procedures to determine the safety and tolerability of their assigned (randomized) study medication. Patients will be instructed to take a pouch from their assigned Patient Kit, open it and self –administer the medication in the clinic. The patient should administer the dose while sitting or in a semi-supine position. They will be assessed and monitored pre-dose and following dosing for the next 2 hours as follows:

- 12-lead ECG in triplicate at pre-dose and 2, 30, 60, 90, and 120 min post dose
- Adverse Event assessment
- Brief Physical examination at 120 min post dose

Patients who meet all inclusion criteria and none of the exclusion criteria and have no clinically-significant observations or abnormalities on the ECG following administration of Study Medication (either 1 mg AZ-010, 3 mg AZ-010, or placebo) will be provided with their Patient Kit that contains 5 unused Staccato devices in addition to the 1 Staccato device that was used in the clinic.

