9.4 ELECTROCARDIOGRAM

The change from baseline in electrocardiogram intervals (PR, QT, QTcF, QRS, and RR) to each scheduled assessment will be summarized descriptively by dose group. Baseline will be defined as the last ECG obtained on Visit 2 and prior to any study medication administration. The number and percentage of participants who have a clinically notable ECG interval abnormality or other clinically significant ECG finding will be summarized. In addition to descriptive statistics of change from baseline, the number and percentage of participants with QTcF intervals > 450, > 480 and > 500 msec. as well as those with changes from baseline > 30 msec. and >60 msec. will be provided for

each treatment group at each timepoint. A listing of abnormal ECG values will also be provided. For ECGs collected in triplicate, the average value will be used.

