Antiemetic agents have been reported to be a key component of support care for acute abortive treatment during the prodromal and emetic phases of CVS in adults (Abell et al, 2008). Abortive IV antiemetic agents such as the 5-HT3 antagonist ondansetron at high doses (0.3–0.4 mg/kg up to 24 mg, q. 4–6 hours) and granisetron (10 μ g/kg, q 4–6 hours) were reported for supportive treatment of acute vomiting episodes in CVS patients (Li and Misiewicz et al, 2003; Yang, 2010; Venkatasubramani, 2007). Despite the widespread use of 5-HT3 antagonists in the treatment of CVS, there have been no definitive clinical trials conducted to date.

Alexza Pharmaceuticals (Alexza) is currently developing *Staccato*® Granisetron for Inhalation (*Staccato* Granisetron; AZ-010) as an acute treatment of CVS. *Staccato* Granisetron represents a new dosage form of granisetron. It is a single-use, hand-held, drug-device combination product that delivers aerosolized granisetron. From a drug development perspective, one of the most compelling characteristics of *Staccato* Granisetron is that the drug can be delivered non-invasively with rapid IV-like pharmacokinetics to individuals. In previous clinical studies with *Staccato* Granisetron and a number of drugs using the *Staccato* technology, mean peak plasma concentration was achieved within minutes following inhalation. In a first-in-human, single ascending dose study with *Staccato* Granisetron (AMDC 010-101; refer to CSR: IND 145,487 SN 0009), the median time to maximum plasma concentration was approximately 2 minutes for doses ranging from 0.5–3 mg.

Staccato Granisetron may provide significant benefit for the treatment of CVS since it has rapid pharmacokinetics and bypasses GI absorption of the drug. Because of the simplicity of the delivery, the patient is only required to take a normal breath for delivery of the aerosolized drug. Consequently, inhalation via *Staccato* delivery could provide a non-invasive, rapid delivery of granisetron and lead to a more rapid and effective control of acute vomiting episodes, representing an improvement to existing patient care. Consequently, this study (AMDC 010-201) is designed to assess the effects of *Staccato* Granisetron as an acute treatment during an episode of CVS in patients with moderate to severe disease.

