10.4 Electrocardiogram

Twelve-lead electrocardiograms will be performed after the patient has rested in a supine or semi-supine position for at least 5 minutes. Individual parameters including heart rate, PR, QT, QTcF, QRS, and RR intervals will be collected. Repeat electrocardiograms (if deemed necessary) should be performed at least 5 minutes apart. The Investigator should indicate review of the electrocardiogram report by signing and dating the report. ECGs performed on Day 1 for pre-test assessment will be collected in triplicate for the pre-dose and post-dose collection times. The initial ECGs should be performed in a semi-supine position to accommodate appropriate dosing of the product.

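### The Visit 2 dose may be taken sitting, but a seated doser cannot have the 5 minutes' recumbent rest required before the ECG due 2 minutes later

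*Combined protocol and SAP*

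**What the plan says.** Protocol 7.6.2 governs the test dose at Visit 2. On posture it says "The patient should administer the dose while sitting or in a semi-supine position", and on monitoring it lists "12-lead ECG in triplicate at pre-dose and 2, 30, 60, 90, and 120 min post dose". Footnote 7 to the Schedule of Events (protocol 7.5) repeats those times and attaches no window to any of them.

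Protocol 10.4 sets the recording conditions: "Twelve-lead electrocardiograms will be performed after the patient has rested in a supine or semi-supine position for at least 5 minutes". SAP 5.9.4 repeats this rest rule. Neither section exempts the 2-minute recording. Protocol 10.4 ends with a further instruction: "The initial ECGs should be performed in a semi-supine position to accommodate appropriate dosing of the product". SAP 5.9.4 does not carry that sentence.

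On exposure, protocol 4.1 reports from the first-in-human study that "the median time to maximum plasma concentration was approximately 2 minutes". Protocol 7.4 describes inhaled and IV granisetron as "both treatments yielding peak exposure within 2 minutes".

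SAP 9.4 takes the last pre-dose ECG at Visit 2 as baseline. At each timepoint it counts QTcF values above 450, 480 and 500 msec, together with "those with changes from baseline > 30 msec. and >60 msec".

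**The concern.** Two instructions apply to the same recording, and a participant who uses a permitted dosing position cannot satisfy both. Sites would have to choose between them. They could wait for the full rest, so that the recording misses its time, or record on time without the rest. Different sites may choose differently.

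The conflict falls on the one ECG placed near peak exposure; the next is at 30 minutes. That ECG has three uses:

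- It is one of five post-dose recordings that decide whether the participant goes home with the five unused devices (protocol 7.6.2).
- A clinically significant abnormality on these recordings ends participation and removes the participant from the efficacy analyses (SAP 6.9.1.3, intercurrent event 1).
- It supplies the 2-minute QTcF change and outlier counts in SAP 9.4.

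For a seated doser, the individual 2-minute change from baseline may therefore be off the peak or may include an effect of the posture change.

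**Working it through.** The plan gives no figure to reproduce here. The check is timing arithmetic on stated inputs.

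**Inputs**

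- Dosing position: sitting or semi-supine (protocol 7.6.2).
- Post-dose ECG times: 2, 30, 60, 90 and 120 minutes (protocol 7.6.2; 7.5, footnote 7).
- Required rest: R = 5 minutes or more, supine or semi-supine (protocol 10.4; SAP 5.9.4).
- Median time to peak concentration: about 2 minutes (protocol 4.1).
- Planned number randomized: 150 (protocol 7.2).

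**Seated doser**

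If the dose is taken sitting at time 0, recumbent rest can start no earlier than time 0. At an ECG due at time T, the rest is therefore at most T.

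- At T = 2: rest ≤ 2 minutes, so the shortfall is at least 5 − 2 = 3 minutes.
- Earliest ECG that meets the rest rule: 5 minutes after dosing or later. That is at least 3 minutes behind schedule and after the median peak.
- At T = 30, 60, 90 and 120: there is ample time for 5 minutes' rest, so no conflict arises.

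One of five post-dose timepoints is affected.

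**Semi-supine doser**

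Suppose the participant rests semi-supine for at least 5 minutes before the pre-dose triplicate and keeps that position through dosing. Rest at the 2-minute ECG is then at least 5 + 2 = 7 minutes, and both rules are met.

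**How many participants**

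The documents do not say how many would dose seated, so the range is 0 to 150. As assumptions only:

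| Share dosing seated | Participants affected |
|---|---|
| 10% | 0.10 × 150 = 15 |
| 25% | 0.25 × 150 = 37.5, about 38 |
| 50% | 0.50 × 150 = 75 |

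**Size in msec**

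This cannot be derived. The documents give no posture effect on QTcF and no concentration at 5 minutes to set against the peak.

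**The case against.** The strongest reply is that protocol 10.4 already deals with this. Its last sentence ties the posture of the initial ECGs to dosing, so the authors saw the interaction, and a site that reads both sections has an obvious compliant route. That stands as far as it goes: participants who follow that route are not affected. But the sentence governs posture for the ECG. It does not withdraw the sitting option in 7.6.2, which is the section that sets out the Visit 2 dosing procedure. Nor does it say that the position must be held from the pre-dose triplicate through the 2-minute one.

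A second reply is that the rest rule does not call for uninterrupted rest. The participant has already rested for the pre-dose triplicate, and dosing takes one breath and a breath hold of up to 10 seconds (protocol 17.2). The text does not expressly exclude this reading. It is strained, however, for a rule about the participant's condition before an ECG is recorded, when the participant has since sat up.

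A third reply is that no consequence has been shown. Safety summaries are descriptive, four of the five post-dose ECGs are sound, and no wrong release or wrong exclusion has been demonstrated. All of that is true, and it is why the point is minor. Dosing position is also chosen under blinding, so the comparison with placebo should not be biased.

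**Conclusion.** The concern holds, as a minor point. A participant who takes the clinic dose sitting, as 7.6.2 permits, is at least 3 minutes short of the required rest at the 2-minute ECG. The alternative is to have that ECG at least 3 minutes late.

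This rests on reading the rest rule as rest immediately before each ECG, and on the 2-minute time having no window, since none is stated. The practical extent depends on how many participants dose seated, which the documents do not give. Whether the effect on any individual QTcF reading is material is unknown.

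**What to change.** In protocol 7.6.2, remove sitting as an option for the clinic dose. State that the dose is taken semi-supine, in the position held since the pre-dose ECG triplicate and kept until the 2-minute triplicate is complete.

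Semi-supine dosing is already allowed and already agrees with 10.4, so no procedure, ECG, visit or analysis is added. The cost is one sentence. Under protocol 13.4 the change must go through a protocol amendment with IRB approval.

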Randomized participants without clinical observations in the 2-hour observation period will be asked to treat a subsequent CVS episode (with single daily dosing up to 5 consecutive days) within 12 weeks after the randomization date. Enrolled participants will self-administer the study medication when they know their CVS episode is imminent or as soon as possible after a CVS-related vomiting episode has begun. Participants will interact with their ePD prior to initiation of treatment (if possible) and to capture the study data. The ePD will be used to record the date and time of study medication administration, the number of vomiting and retching events, and the participant reported outcome measures (including the intensity and duration of the CVS episode, severity of abdominal pain, nausea, and anxiety/panic, and characteristics of the nausea, vomiting and retching over defined time periods) (section 5.8). Participants will also record the number of vomiting and retching events in the 24 hours after dosing on a paper questionnaire.

Participants will be instructed to contact the Research Clinic at the earliest possible time after initiation of dosing and at any time should they require rescue medication, medical assistance or experience an intolerable AE at home during the treatment period. Participants will record rescue medications taken after administration of study medication in their ePD and on a paper concomitant medications form. Rescue medication may include any agent(s) from the list described in Section 9.8 of the protocol. Participants are encouraged to avoid rescue medication for the first 2 hrs. following treatment with the study medication.

Participants will be required to return to the Research Clinic (Visit 3) within 3-5 days from the last study medication administration for final in-clinic assessments, to return the Patient Kit containing the used and unused study medication, ePD, and any other unused supplies. Conversely, participants will be asked to return to the Research Clinic after 12 weeks with their unused Patient Kit if they did not treat a CVS episode within this time period.

Visit 3 will include the following assessments: Vital signs; full physical examination; assessment for treatment emergent adverse events; 12- lead ECG, concomitant medications (including rescue medication taken), and clinical labs.

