5.9 SAFETY

Safety and tolerability of AZ-010 will be assessed by evaluating adverse events, vital signs, clinical laboratories, ECG results, as well as physical examinations.

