9.3 VITAL SIGNS

The mean change from baseline to each scheduled assessment will be summarized descriptively by dose group for each vital sign variable specified in the protocol. Baseline will be defined as the last vital sign value obtained on Visit 2 and prior to any study medication administration.

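### No post-dose blood pressure, respiratory rate, pulse oximetry or temperature is scheduled in the 2-hour clinic observation, so the SAP 9.3 table cannot show an acute, exposure-related effect on them

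*Combined protocol and SAP*

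**What the plan says.** Both documents name vital signs as a safety measure: "Safety and tolerability of AZ-010 will be assessed by evaluating adverse events, vital signs, clinical laboratories, ECG results, as well as physical examinations" (SAP 5.9; the same list is in protocol 12.4.2).

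Protocol 7.6.2 divides Visit 2 into two lists.

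- The arrival list, completed before the clinic dose, includes "Vital signs measured with the subject in a seated position (for at least 2 minutes prior), including blood pressure, pulse rate, respiration rate, pulse oximetry," with temperature as the last item.
- The list for the clinic dose itself opens with "They will be assessed and monitored pre-dose and following dosing for the next 2 hours as follows". It has three items: "12-lead ECG in triplicate at pre-dose and 2, 30, 60, 90, and 120 min post dose", "Adverse Event assessment", and a brief physical examination at 120 minutes. Vital signs are not on it.

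Table 1 (SAP 5.5 and protocol 7.5) marks vital signs once each at Visits 1, 2 and 3, and not on home dosing days. The Visit 2 ECG entry has a footnote giving post-dose times. The vital-signs entry has no footnote.

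Visit 3 takes place "within 3-5 days from the last study medication administration for final in-clinic assessments" (SAP 5.3), or after 12 weeks for someone who treated no episode. SAP 9.3 describes, by dose group, how each vital sign moves from baseline to every later planned measurement: "Baseline will be defined as the last vital sign value obtained on Visit 2 and prior to any study medication administration".

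On pharmacokinetics, protocol 4.1 gives a median time to peak of about 2 minutes, and protocol 7.4 states: "The half-life was the same with the IV and Staccato treatments at 10 hr".

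**The concern.** The product is inhaled, reaches the deep lung and peaks within minutes. The participant then stays in clinic for 2 hours with staff recording five post-dose ECGs. In that window the plan asks for no blood pressure, respiratory rate, oxygen saturation or temperature. The next scheduled values come when almost all of the drug has gone.

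The stake is how the vital-sign table is read. Three arms with similar changes at Visit 3 could be taken to mean that dosing does not disturb vital signs, although the table holds no scheduled value from the hours after a dose. It also mixes two groups. The Safety Population is everyone who received study drug (SAP 6.4), and every dosed participant takes the clinic dose, so it includes people who never treat at home. Their Visit 3 value relates to one dose about 12 weeks earlier. SAP 9.3 neither separates nor labels them.

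**Working it through.** The documents give no figure to reproduce here; the sample size was not based on power. The check is a reading of the schedule followed by half-life arithmetic.

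**1. What is scheduled**

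| Place | Vital signs | ECG |
|---|---|---|
| Protocol 7.6.2, arrival list | Yes, pre-dose | Not listed |
| Protocol 7.6.2, list for the clinic dose | None | Pre-dose and 2, 30, 60, 90, 120 min |
| Table 1, home dosing days | None | None |
| Protocol 7.6.4, Visit 3 | Yes | Yes |

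Scheduled post-dose measurements in the 2-hour window: five ECGs and no vital-sign set. Scheduled vital-sign sets after the SAP 9.3 baseline: one, at Visit 3.

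**2. Inputs for timing**

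- Half-life 10 h (protocol 7.4, healthy volunteers).
- Visit 3 at 3 to 5 days: 3 × 24 = 72 h to 5 × 24 = 120 h.
- No episode treated: 12 × 7 × 24 = 2,016 h after the clinic dose.
- Home dosing once daily, at most 5 doses (protocol 9.1).

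**3. Drug remaining at Visit 3**

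Half-lives elapsed = hours / 10. Fraction remaining = 0.5^(hours / 10), assuming one-compartment decay.

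- 72 h: 7.2 half-lives; 0.5^7.2 = 0.0068, or 0.68%.
- 120 h: 12 half-lives; 0.5^12 = 0.00024, or 0.024%.
- 2,016 h: 201.6 half-lives; effectively nothing.

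**4. Accumulation over five daily doses**

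Factor = sum of 0.5^(24i/10) for i = 0 to 4 = 1.23. Relative to the starting level after one dose, what remains is 0.84% at 72 h and 0.030% at 120 h. Repeat dosing does not change the picture.

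**5. Sensitivity to the half-life** (5, 15 and 20 h are assumptions, not figures from the documents)

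| Half-life | Half-lives elapsed, 72 to 120 h | Remaining, 72 to 120 h |
|---|---|---|
| 5 h | 14.4 to 24 | below 0.01% |
| 10 h (stated) | 7.2 to 12 | 0.68% to 0.024% |
| 15 h | 4.8 to 8.0 | 3.6% to 0.4% |
| 20 h | 3.6 to 6.0 | 8.2% to 1.6% |

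**6. The same sum at the existing ECG times**

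- 2 min: 0.033 / 10 = 0.0033 half-lives, 99.8% remaining.
- 120 min: 2 / 10 = 0.2 half-lives, 87% remaining.

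Any of the ECG times already planned would give a value during exposure.

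**The case against.** The best defence is that this is a design choice and no passages conflict over the timing. The acute risk the plan singles out is ECG abnormality, with QT prolongation named, and the 2-hour window is built densely around it. Adverse events are assessed, there is an examination at 120 minutes, and kits go home only if nothing clinically significant is seen. Two Phase 1 studies covered doses up to 3 mg (protocol 4.4). Acute vital signs may be described in the Investigator Brochure, which is not available here. All of this stands and limits the importance of the point. It does not supply between-arm data on blood pressure, respiration, saturation or temperature after a dose.

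Four stronger readings are tempting, and the documents do not support them.

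- **No vital sign is ever measured on drug.** Heart rate and RR are collected at each post-dose ECG (protocol 10.4), and SAP 9.4 tabulates change in RR. Early termination repeats the Visit 3 assessments with no fixed interval from dosing (protocol 8.3.1), so some values could fall nearer a dose. These would be unscheduled and selective.
- **The table can show no effect at all.** A lasting or delayed change could still be present at Visit 3.
- **The measurement misses an expected effect.** The documents name no expected effect on blood pressure, respiration or saturation.
- **The table is bound to mislead.** Safety summaries are descriptive and the Visit 3 timing is stated openly. Misreading is a risk that labelling removes.

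There is also a practical objection. New measurements need a protocol amendment with IRB approval (protocol 13.4). The SAP is final and dated 03 March 2022, and the synopsis estimated the last participant would complete in December 2021. It may be too late to collect them.

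**Conclusion.** The point holds in limited form. No blood pressure, respiratory rate, pulse oximetry or temperature is scheduled in the 2 hours after the clinic dose. The single scheduled post-baseline set falls 7.2 to 12 half-lives after the last dose, with under 1% of drug remaining, or about 12 weeks after the clinic dose if no episode was treated. SAP 9.3 therefore cannot show an acute, exposure-related effect on these measures, and it pools two groups with very different intervals since dosing. The documents do not say how many participants are expected to go untreated, so the degree of mixing is unknown.

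The percentages assume one-compartment decay and a healthy-volunteer half-life. At an assumed 20 h the remainder is still only 8.2% to 1.6%. The schedule reading depends on neither assumption.

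Efficacy, the primary endpoint and the ECG evaluation are unaffected. This is an inexpensive improvement to a named measure of a primary objective, not a flaw that undermines the trial.

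**What to change.** **If participants are still to be dosed in clinic:** amend protocol 7.6.2 and Table 1 to repeat the existing vital-sign set, including pulse oximetry, alongside one or more of the post-dose ECG times already planned. The sponsor should choose the times. In SAP 9.3, summarise change from the Visit 2 pre-dose value to those times by arm.

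**In any case:** in SAP 9.3, split the Visit 3 vital-sign table by treated at home yes/no, label it as off-drug, and state that no acute post-dose vital signs other than ECG heart rate were scheduled. If the SAP is not reissued, record this in the clinical study report, which SAP 3 already requires for changed analyses.

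**Reconcile the definition:** protocol 10.2 leaves pulse oximetry out of vital signs, while SAP 5.9.3 and protocol 7.6.1, 7.6.2 and 7.6.4 include it.

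**Cost:** the new measurements need an amendment, IRB approval, an eCRF change, and a few minutes and extra data points per participant, with staff already present for the ECGs. The split and labelling need only minor wording and programming.
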